Data from randomized clinical trials and observational studies suggest relapse is common if rituximab is discontinued indefinitely. Among patients in the RAVE trial who achieved complete remission following treatment with rituximab, 32% had a relapse within 18 months(9).

Furthermore, Alberici *et al* reported that 41% of patients who received maintenance rituximab every 6 months for 24 months relapsed at a median of 34.4 months following discontinuation of therapy(17). Predictors of relapse included return of B cells and change from ANCA negativity to positivity(17).

Survival of ANCA vasculitis patients undergoing rituximab-induced continuous B cell depletion

A prospective and longitudinal clinical trial is needed to determine the ideal treatment strategy for long-term maintenance of remission. Here we propose to compare 2 strategies once patients have

been in sustained remission on scheduled rituximab dosing with a goal of undetectable B cells for greater than or equal to 2 years. Target enrollment is 200 subjects over 48 months from the time the first patient is enrolled to be followed for a common close out date of 36 months after the last subject is enrolled.

The study design is an open-label, single center, randomized and two-arm controlled trial to evaluate the optimal maintenance of remission strategy that provides the best relapse-free survival in patients with ANCA vasculitis as determined by relapse-free remission at 18, 24 and 36 months from enrollment. Subjects with ANCA vasculitis in sustained remission on regularly scheduled rituximab infusions with a goal of undetectable B cells for a minimum of two years who meet specific entry criteria will be randomized with stratification based on ANCA subtype and rituximab vintage (i.e., duration of continuous rituximab prior to enrollment) to one of two arms :

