Rituximab (Rituxan, Genentech), which is FDA-approved for GPA and MPA, will be used in the study.

C. Devices to be used

Not applicable

D. Procedures/surgical interventions

Not applicable

E. Data to be collected and when the data is to be collected

At present, there is no standard of care for maintenance of remission in ANCA vasculitis beyond the two-year mark; thus, the role of continuous versus intermittent B cell depletion requires investigation. Efficacy and toxicity are the foci of our outcome analysis for this study and will be assessed through analysis of primary and secondary endpoints.

The following variables will be collected at EACH study visit:

1. VDI (every 6 months)
2. Modified BVAS/WG
3. Laboratory data at baseline and at subsequent visits
 - a. Complete Blood Count
 - b. Comprehensive Metabolic Panel
 - c. eGFR
 - d. ANCA titer
 - e. ESR
 - f. CRP

- g. Immunoglobulin levels (every 6 months)
 - h. Urinalysis
 - i. Urine Hcg for women of child bearing potential (only at screening and when reinfused with rituximab)
 - j. Flow cytometric analysis of peripheral B and T lymphocyte markers
4. Concomitant medications at each visit
 5. Adverse events assessment

VI. Biostatistical Analysis

A. Specific data variables being collected for the study (e.g. data collection sheets)

Data variables collected are listed above and we will also verify contact information at each visit to ensure appropriate follow-up.

B. Study endpoints

Primary endpoints:

1. Disease flare defined as a BVAS/WG ≥ 2 . A subgroup analysis will be performed by ANCA subtype.

Secondary endpoints:

1. Proportion of patients with serious adverse events (SAEs), including all episodes of Late Onset Neutropenia (LON, absolute neutrophil count < 1000 cells/mm³)
2. The composite of disease flare (defined as BVAS/WG ≥ 2) and serious adverse events.
3. Total rituximab utilization during the study period
4. Accrued organ damage as assessed by the Vasculitis Damage Index (VDI)
5. Patient quality of life assessment using the SF-36v2 and EQ-5D-5L surveys every 6 months
6. Number of major (modified BVAS-WG ≥ 3) relapses
7. Survival
8. Hypogammaglobulinemia (IgG < 400 mg/dL)
9. All infections

C. Statistical methods

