Data will be analyzed by the intention-to-treat principle. Randomization will be stratified on ANCA subtype (MPO vs PR3) and rituximab vintage (< 3 years vs > 3 years). Rituximab vintage is the duration of continuous rituximab therapy administered prior to enrollment in the study. We have contracted with the company StudyTRAX to perform randomization on stratified variables via random permuted blocks.

Continuous data will be summarized using descriptive statistics. Continuous data will be assessed using the t-test or Wilcoxon rank-sum test as appropriate. Categorical data will be assessed using the Chi-square and the Fisher exact tests as appropriate. The probability of remaining free of relapse will be estimated using the Kaplan-Meier method. The difference between the two

treatment strategies will be assessed using the log-rank test. *P* values of 0.05 will be considered significant.

D. Power analysis

Using a two-sided logrank test with an alpha level of 0.05, a projected relapse risk of 15% in the superior group and 30% in the inferior group, and an estimated enrollment time of 36 months, it was determined that 180 patients are required to detect a significant difference with a power of 0.80. We aim to enroll 200 patients in the study.

VII. Risks and Discomforts

Subjects may experience side effects while receiving rituximab, which is given as part of their regular medical care for their GPA or MPA. As per the entry criteria, subjects have been on rituximab for 2 years prior to enrollment, the side effects have been discussed in detail and a signed consent for rituximab is obtained for every patient receiving rituximab at the first dose and annually thereafter.

The effects of rituximab on a fetus are unknown and may be harmful. Individuals of childbearing potential should use effective birth control during treatment and for 12 months after their last rituximab infusion. Prior to any infusion of rituximab to a woman of childbearing potential, a urine pregnancy test is performed and recorded. If a woman is found to be pregnant, she will then be removed from the study and followed based on best medical judgment as deemed appropriate by the clinician investigator.

A. Complications of surgical and non-surgical procedures

Not applicable

B. Drug side effects and toxicities

Common side effects of Rituxan

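### Rituximab totals, infection counts and SAE proportions are compared without time at risk, while the withdrawal rule may shorten observation in the arm with more flares

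*Combined protocol and SAP*

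**What the plan says.** Section VI.B lists among the secondary endpoints "Total rituximab utilization during the study period", all infections, and "Proportion of patients with serious adverse events (SAEs", with every episode of late-onset neutropenia (LON) included). Section IX.C restates infections as a number. None has a time denominator.

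Section VI.C does not assign a test to each endpoint. Its general rules are "Continuous data will be assessed using the t-test or Wilcoxon rank-sum test as appropriate" and "Categorical data will be assessed using the Chi-square and the Fisher exact tests as appropriate". Kaplan-Meier is tied to freedom from relapse, and the log-rank sentence follows from it. No rate, offset, fixed window or competing-event method appears.

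Two statements govern how long a patient is observed. The design text in section I has subjects "followed for a common close out date of 36 months after the last subject is enrolled", and section V.A continues visits to that date. Section IX.B removes subjects from the study for a modified BVAS-WG of 2 or more, and also for prednisone above 7.5 mg daily, low IgG, low WBC or a serious infection needing hospitalization. Intention-to-treat is named in VI.C, but there is no rule on data after withdrawal.

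**The concern.** If observation ends at flare, the strategy that prevents more flares keeps its patients under observation longer. Those patients then have more time to receive rituximab, acquire infections and have an SAE. A t-test on totals or a chi-square test on proportions reads the extra time as extra drug use or extra toxicity.

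Secondary Aims 1 and 3 ask which strategy has more SAEs and which uses more rituximab, the latter for cost. The distortion works against the strategy that better prevents relapse, and that trade-off is what the trial is meant to settle.

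**Working it through.** **Inputs from section VI.D.** The log-rank test is two-sided at 5%. The planning effect is "a projected relapse risk of 15% in the superior group and 30% in the inferior group". Accrual is taken as 36 months, and the resulting sample size is given as "180 patients are required to detect a significant difference with a power of 0.80". Section I gives accrual of 48 months, section IV.B 36 months. Follow-up is therefore planned at 36–84 or 36–72 months.

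**Assumptions.** The risks apply at 36 months (no time point is stated), hazards are constant, accrual is uniform, allocation is 1:1 with 100 per arm, and observation runs from randomisation to flare or close-out. The documents give no event rates for rituximab courses, infections or SAEs, so a range is shown.

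**1. The plan's own figure.** The hazards are h = −ln(0.85)/3 = 0.0542 and −ln(0.70)/3 = 0.1189 per year, a ratio of 2.19. Freedman's formula gives (3.19/1.19)² × (1.96 + 0.84)² ≈ 56.1 events. With 36-month accrual plus 36 months, the flare probabilities are 0.215 and 0.411, mean 0.313, so N = 56.1/0.313 ≈ 179. This matches 180 and supports reading the risks as 36-month risks.

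**2. Mean observation.** With accrual of A years, P(flare before close-out) = 1 − (e^(−3h) − e^(−(3+A)h))/(A·h), and mean observation = P/h.

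| Accrual | Fewer flares | More flares | Shortfall |
|---|---|---|---|
| 48 months | 0.2358/0.0542 = 4.35 y | 0.4429/0.1189 = 3.73 y | 14% |
| 36 months | 0.2155/0.0542 = 3.98 y | 0.4112/0.1189 = 3.46 y | 13% |

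At one event per year in both arms, mean totals under 48-month accrual are therefore 4.35 and 3.73 per patient.

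**3. Totals, equal true rates (simulation).** Poisson counts at 0.5–1.5 per year: the t-test or Wilcoxon rejects in about 21–47% of trials across the two accrual lengths. Wilcoxon detail:

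| Setting | 0.1/y | 0.5/y | 1.0/y |
|---|---|---|---|
| Stop at flare, 48-month accrual, Poisson | 11.2% | 28.6% | 41.2% |
| Same, overdispersed counts | 9.8% | 20.8% | 24.3% |
| All followed to close-out, 48-month accrual, Poisson | 5.1% | 4.6% | 4.7% |

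A person-time comparison (ratio of total events to total time, with robust variance) rejects in about 5–6% when observation stops at flare. If relapse risk is equal in both arms (22.5%), the raw tests hold 4.6–5.4%.

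**4. SAE proportions, equal true hazard s.** For planned follow-up u, the proportion observed with an SAE is s/(s+h) × (1 − e^(−(s+h)u)), averaged over u. At s = 0.10 with 48-month accrual this gives 34.4% against 29.9%; with everyone followed to close-out it is about 39% in both arms. Two-proportion rejection is 7–15% for s = 0.05–0.20 across the accrual lengths.

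**5. Shorter schedule.** Visit 16 falls 6 + 14 × 3 = 48 months after Day 0, about 42 months after enrolment. If follow-up stopped there, chi-square rejects in 6.5–21.0% and Wilcoxon in 6.2–21.2% at 0.05–1.0 events per year.

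**The case against.** **The documents do not settle that observation ends at flare.** Intention-to-treat, visits to a common close-out, treatment of flares at the investigator's discretion, and endpoints such as survival and accrued damage all fit continued follow-up. If follow-up does continue, the stated tests keep their level. This stands: the point is conditional on the IX.B wording, which is the only text saying what happens to a subject after a flare qualifies for withdrawal.

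**Staggered entry is not the cause.** A reader might infer that follow-up varying from 3 to 7 years is itself enough to bias the tests. It is not, because randomisation balances entry dates. It adds noise only: the variance of a Poisson total rises by the factor 1 + rate × Var(u)/E(u), which is 1.17–1.40 at 1–1.5 courses per year.

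**Not every secondary endpoint is affected.** A reader might extend the bias to the flare-or-SAE composite or to major relapses. In the composite, the flare that ends observation already counts as an event. A major relapse (BVAS-WG of 3 or more) also meets the withdrawal threshold, so on this reading each patient has at most one and the better arm has fewer.

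**Equal rituximab rates are unlikely,** since the two arms have different triggers and courses. This stands as well. For rituximab the likelier harm is a distorted or masked difference rather than a false one.

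**Other withdrawal reasons also shorten observation,** possibly more in the more heavily dosed arm. This was not simulated, and it leaves the net direction less certain.

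**Conclusion.** The concern holds in a limited form. If subjects leave observation at flare, as IX.B reads, and relapse differs between arms as the trial is powered to detect, the planned comparisons of total rituximab use, number of infections and proportion with SAEs partly measure time observed. The effect is modest for rare SAEs and large for frequent outcomes. The ranges rest on assumed event rates, constant hazards and the 36-month reading of the planning risks; overdispersion brings the figures for totals down to about 10–25%.

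The primary log-rank comparison is outside this point. Nor do the documents support saying that totals can never be converted to yearly use: adverse events and concomitant medications are recorded at each visit, so the ingredients should be available. What is missing is an analysis that uses them.

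**What to change.** In VI.C, replace the general tests for these endpoints:

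1. **Rituximab use and infections:** rate per patient-year from randomisation, by negative binomial or quasi-Poisson regression with a log person-time offset, arm and the two stratification factors; report the rate ratio with 95% CI.
2. **SAEs and LON:** time to first event, compared by cause-specific Cox or log-rank with censoring at end of observation. Do not use a raw proportion, or a cumulative incidence with flare as competing event, for this comparison: the latter reproduces the 34.4% against 29.9% gap.
3. **Composite and major relapses:** time to first event suits both; a recurrent-event rate model does not.
4. **Observation:** reconcile the IX.B withdrawal wording with intention-to-treat (VI.C) and follow-up to common close-out (I, V.A), and state whether data collection continues after withdrawal. Reconcile the 36- and 48-month accrual figures and the numbered visits at the same time.

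The cost of items 1–3 is SAP wording, provided that dates of infusions, adverse events and last contact are held; confirm this. The downside is small: the offset assumes roughly constant rates, and both the offset and the censoring assume that stopping at flare is non-informative. The SAP should state these assumptions.

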- 1. Intermittent B cell depletion with rituximab re-dosing upon B cell return:** Subjects will no longer receive regularly-scheduled every six-month doses of rituximab and will instead be seen in clinic with B cell monitoring every 3 months (beginning 6 months after their last rituximab dose). B cell levels will be determined by the number of CD20 positive cells detected by peripheral blood flow cytometry. Subjects will not receive rituximab if the B cell level remains < 10 cells/mm³. Once peripheral B cells levels rise to ≥ 10 cells/mm³, they will receive rituximab 1000 mg IV x 1 dose. If patients receive rituximab they will become B cell depleted, but will stay on their original study schedule. Following B cell depletion, subjects will be seen in clinic every three months, and B cell monitoring every 3 months will continue as scheduled. Patients will continue to be dosed with rituximab each time the B cell count rises to 10 cells/mm³. In the unique scenario that the B cells are detectable, but less than the threshold of 10 cells/mm³, subjects will be asked to return in 6 weeks for repeat B cell testing.

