- 2. Hold continuous dosing with rituximab with re-dosing upon significant ANCA titer increase:** Subjects will no longer receive regularly scheduled every six-month doses of rituximab, and will instead be seen in clinic with the ANCA titer monitoring every three months (beginning 6 months after their last rituximab dose). For MPO, a significant increase will be defined as a 5-fold rise in ANCA titer and a level greater than 4 times the cutoff value for the assay. For PR3, a significant rise will be defined as a 4-fold rise in ANCA titer to a level at least twofold above the cutoff value for the assay. Patients who sustain a significant increase in ANCA titer will receive rituximab 1000mg IV x 2 doses (~2-3 weeks apart). If the ANCA titer then falls to less than twofold above baseline or falls below the specified threshold (the cutoff value of the assay for PR3 and 4 times the cutoff value for MPO) after rituximab, patients will be seen in clinic every three months, with monitoring of ANCA titers. However, if the ANCA titer remains twofold above baseline and above the specified threshold (the cutoff value of the assay for PR3 and 4 times the cutoff value for MPO) after rituximab, patients will continue to receive rituximab 1000mg IV every 6 months for a maximum of 2 doses, at which time a new baseline ANCA titer will be established. Once the new baseline ANCA titer is established, the patients will continue to be seen in clinic every 3 months, with monitoring of ANCA titers. Patients will continue to be dosed with rituximab each time they meet criteria for a significant ANCA titer rise. In this arm, rituximab administration is not contingent upon B cell levels. Rituximab will only be dosed based on the ANCA titer as described above. Baseline ANCA titer will be recalculated to an average of the two highest of the last four values if all four are less than the original baseline. Patients in

the ANCA arm will move to once yearly CD20 testing after CD20 levels return to normal levels (>90 cells/uL).

Patients can be treated at any time during the study period with a total prednisone dose of ≤ 7.5 mg. Patients with a disease flare (defined by BVAS/WG ≥ 2) will have reached the primary endpoint and will be treated for relapse at the discretion of the investigator

II. Specific Aims

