- 1. Primary Aim: To determine whether a rituximab-dosing protocol based on: 1) reconstitution of peripheral B cells or 2) a serologic ANCA flare is more efficacious in preventing relapse in patients with ANCA vasculitis.** Eligible patients will have completed a minimum of 2 years of rituximab maintenance therapy without relapse. The endpoint will be disease relapse defined as a BVAS/WG ≥ 2 . Analysis will also be stratified based on ANCA subtype (due to differences in relapse between patients with MPO and PR3 ANCA) and rituximab vintage.
- 2. Secondary Aim 1: To determine whether a rituximab-dosing protocol based on: 1) reconstitution of peripheral B cells or 2) a serologic ANCA flare is associated with more serious adverse events.** Serious adverse events of interest include those related to vasculitis activity and those that develop as a consequence of rituximab therapy. The main rituximab-associated serious adverse events noted in our cohort are infection, late-onset of neutropenia, and infusion reactions(10)
- 3. Secondary Aim 2: To determine whether a rituximab-dosing protocol based on: 1) reconstitution or peripheral B cells or 2) a serologic ANCA flare is associated with a greater composite of disease relapse (BVAS/WG ≥ 2) and serious adverse events.**
- 4. Secondary Aim 3: To determine whether a rituximab-dosing protocol based on: 1) reconstitution of peripheral B cells or 2) a serologic ANCA flare is associated with greater rituximab utilization during the study period.** While effective, rituximab therapy is costly and increases health care expenditures. Evaluation of the relative cost of the 2 dosing-strategies will assist in the application of these dosing-strategies to the broad population of patients with ANCA vasculitis.

III. Subject Selection

Patients with ANCA vasculitis who are seen at MGH will be recruited as subjects and inclusion and exclusion criteria are detailed below.

A. Inclusion and exclusion criteria

Inclusion criteria:

1. All patients must be able and willing to give written informed consent and comply with the requirements of the study protocol.

2. Diagnosis: ANCA vasculitis as defined by a positive MPO- and/or PR3-ANCA test together with clinical features characteristic of ANCA-positive diseases as detailed in the 2012 Chapel Hill Consensus Conference Definitions(18).
3. eGFR \geq 20 cc/min/1.73m²
4. Age: 18-82 years old

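### The plan leaves rituximab utilization to a t-test or a Wilcoxon test; because dosing rules shape the arms differently, Wilcoxon could mislead on mean use, the quantity behind the cost aim

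*Combined protocol and SAP*

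**What the plan says.** Section VI.B lists as secondary endpoint 3 "Total rituximab utilization during the study period". Section II, Secondary Aim 3, gives the reason for measuring it: "Evaluation of the relative cost of the 2 dosing-strategies will assist in the application of these dosing-strategies".

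No method is named for this endpoint. Of the general sentences in Section VI.C, the one that fits is "Continuous data will be assessed using the t-test or Wilcoxon rank-sum test as appropriate". It does not say what decides between the tests, which quantity is compared, or over what period.

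Section I sets the dosing. In Arm 1, once B cells reach 10 cells/mm³, "they will receive rituximab 1000 mg IV x 1 dose"; below that count no dose is given. In Arm 2, "Patients who sustain a significant increase in ANCA titer will receive rituximab 1000mg IV x 2 doses", and if the titer then stays high, "patients will continue to receive rituximab 1000mg IV every 6 months for a maximum of 2 doses". Arm 2 patients without a significant titer rise receive none.

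Follow-up runs to a common close-out 36 months after the last enrollment (Section V.A). Patients are withdrawn at a modified BVAS-WG of 2 or more, and for other listed reasons (Section IX.B).

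**The concern.** The drug cost of a strategy is mean drug per patient times the number of patients. A t-test compares means. A Wilcoxon rank-sum test asks whether a random patient in one arm tends to have a higher total than a random patient in the other. The two questions agree when the arms' distributions have the same shape, but need not when the shapes differ.

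Here the protocol's own rules make the shapes differ. Arm 1 builds up in steps of 1 g. Arm 2 is split between patients with no drug and patients with at least 2 g. Many analysts would read the Section VI.C wording as pointing to the rank test for such data. The trial could then report that one strategy uses more rituximab when mean use is the same, overlook a real difference in means, or name the lighter user as the heavier.

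**Working it through.** The plan gives no figure for utilization, so there is none to reproduce.

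**Inputs from the documents.** Target 200 patients (VI.D), so 100 per arm if allocation is 1:1 (the ratio is not stated); dose units as above; two-sided 5% level, taken from VI.D.

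**Assumed, because the documents are silent.** Trigger rates, the share never re-dosed, and mean use.

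**1. Why ranks and means part company.** Suppose 60% of Arm 2 never trigger. The rest have on average 1.5 episodes of 3 g each (2 g plus 0, 1 or 2 g, equally likely). Arm 2 mean = 0.40 × 1.5 × 3 = 1.8 g. Let Arm 1 be Poisson with the same mean of 1.8 g, so its share with no drug is e^(−1.8) = 0.165. Comparing a random Arm 1 patient with a random Arm 2 patient:
- Arm 1 higher, counting only untreated Arm 2 patients: 0.60 × (1 − 0.165) = 0.501.
- Half of the ties at zero: 0.5 × 0.60 × 0.165 = 0.050.
- Sum: 0.55, before adding any wins or ties against treated Arm 2 patients.

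The rank test is centred on 0.50, so it leans towards Arm 1 although the means are equal.

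**2. Rejection rates with equal means, 100 per arm.** Same model; Arm 2 mean = (1 − share never triggered) × 1.5 × 3.

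| Never triggered in Arm 2 | Mean in both arms | Wilcoxon rejects |
|---|---|---|
| 50% | 0.50 × 4.5 = 2.25 g | 46% |
| 60% | 0.40 × 4.5 = 1.80 g | 76% |
| 70% | 0.30 × 4.5 = 1.35 g | 91% |

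With 30% to 40% never triggered and one episode each, Wilcoxon rejects in under 10%. Over all scenarios (30% to 70% never triggered) the range is 5% to 98%. Welch's test rejects in 4% to 6%.

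**3. A second model.** Mean 2 g in both arms, 10% with no drug in Arm 1, treated totals starting at 1 g (Arm 1) or 2 g (Arm 2). With 40%, 50%, 60% and 70% untreated in Arm 2, Wilcoxon rejects in 7%, 24%, 70% and 98%. With 90 per arm the figures are 7%, 23%, 65% and 97%. With 10% untreated in both arms it still rejects in 14%, from the different dose units alone. The t-test stays at about 5%.

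**4. A model with dosing triggers, 3-monthly visits and stopping at relapse.** With nearly equal means between 1.1 and 2.6 g, Wilcoxon rejects in 35% to 96%. The t-test rejects in 3.9% to 5.8%, apart from one run at 7.5% where the simulated means were slightly unequal (1.59 and 1.54 g).

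**5. Control.** When both arms share one zero-heavy distribution, Wilcoxon rejects in 5.0% to 5.7%.

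**6. Unequal means (model of step 2).**
- Arm 2 heavier, 60% never triggered, 1.26 g against 1.8 g: Wilcoxon is significant in about a fifth to a quarter of trials, nearly all naming Arm 1 as the heavier user. Welch has about 45% power.
- Arm 2 heavier, half never triggered, 1.35 g against 2.25 g (2.25/1.35 = 1.67 times): Wilcoxon about 12%, Welch about 87%.
- Arm 1 heavier by 1.5 times: Wilcoxon 92% to 100%, in the right direction.
- Arm 1 heavier by 2 times: both tests reject in essentially 99% to 100%.

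**7. Follow-up.** Enrollment is 36 months in Sections IV.B and VI.D and 48 months in Section I. Planned follow-up therefore runs from 36 months to 36 + 36 = 72 or 36 + 48 = 84 months, less after withdrawal. Neither listed test uses this.

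**The case against.** The strongest reply is that the plan does not assign Wilcoxon to utilization. A reader might infer that it does, but Section VI.C only permits it. It equally permits the t-test, which holds its level at this sample size. That stands: the fault is an unspecified choice, one option of which does not answer the aim.

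A reader might also infer that zeros and skew by themselves break the rank test. They do not, as the control in step 5 shows. The cause is the difference in shape between arms.

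Third, the size rests on assumed trigger rates and on equal or nearly equal means, and nothing in the documents makes equality likely. This also stands. The range runs from no visible problem to near-certain error, and the high figures are not a forecast. If Arm 1 uses about twice the drug of Arm 2, the tests agree. That comfort does not extend to Arm 2 being the heavier user: at 1.67 times, Wilcoxon mostly missed the difference.

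Fourth, Aim 3 is worded as utilization, cost is its rationale, and VI.B has no cost endpoint. Descriptive summaries would probably appear beside any P value. This softens the consequence, but a P value on ranks would still be read as the answer to an aim justified by cost.

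Finally, a rate per patient-year has its own difficulty: withdrawal at relapse shortens follow-up, so exposure time depends on outcome. This is a fair point against offering the rate without a stated counting period.

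**Conclusion.** The point holds as a gap in the analysis of one secondary aim. A test that the plan permits, and that data of this form invite, can give a wrong answer about mean drug use. Under illustrative equal-mean assumptions with 100 per arm, Wilcoxon rejects in about 5% to over 90% of trials, while a comparison of means stays near 5%. It can also miss or reverse a real difference when Arm 2 is the heavier user. These figures depend on trigger rates that the documents do not give. The direction of the problem follows from the dosing rules; its size is unknown. Unequal follow-up and withdrawal are unaddressed whichever test is used.

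The documents do not support reading this as a flaw in the primary analysis. The log-rank comparison and its sample size of 180 do not involve this endpoint.

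**What to change.** In Section VI.C, give utilization its own paragraph:
- Compare mean grams per patient over a defined observation period, and grams per patient-year (total grams divided by total follow-up in each arm).
- Report the between-arm difference or ratio with a Welch or bootstrap 95% confidence interval, or use a quasi-Poisson model with a follow-up offset and robust standard errors.
- State whether drug given after relapse or withdrawal counts, and when each patient's counting period ends.
- Show medians and the proportion never re-dosed as description. Do not base the Aim 3 conclusion on Wilcoxon.

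The cost is wording, plus recording of drug given after withdrawal if that is to count. The interval for a skewed mean may be wider than a rank P value would suggest.
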